5.2.2. Vital Signs Normal/Abnormal Assessments

Change from baseline in **vital signs (blood pressure, respiratory rate, and heart rate)** after the first dose of ProvayBlue™ infusion will be evaluated.

- The secondary efficacy will be the number (%) of patients with concomitant normalization of vital signs (as per the clinical context) within 2 hours, inclusive, after the end of infusion of the first dose of ProvayBlue™
- Time (hours) when the first incidence of normal VS is observed in patients who have abnormal baseline vital signs

The normal ranges used to define normal blood pressure are provided in Table 4. However, in the individual patient narratives, vital signs will be contextualized for comorbidity and other pertinent issues. For example, a patient with chronic obstructive pulmonary disease likely has an elevated respiratory rate even when not suffering for acquired methemoglobinemia; a “return to normal” for such a patient would be clinically expected to differ from “return to normal” for a patient without COPD.

Table 4: Vital Signs Normal Ranges

Population	Systolic Blood Pressure (SBP) mmHg	Diastolic Blood Pressure (DBP) mmHg	Respiratory Rate (RC) Breaths/min	Heart Rate (HR) Beats/min
Birth (12 hours)	60-76	31-45	30-60	120-140
Neonate (96 hours)	67-84	35-53		
Infant (1 to 12 months)	72-104	37-56		
Children (1 to 2 years)	86-106	42-63	22-40	80-110
Children (3 to 5 years)	89-112	46-72	20-28	60-70
Children (6 to 9 years)	97-115	57-76	18-25	70-80
Children (10 to 11 years)	102-120	61-80		
Adolescent (12 to 15)	110-131	64-83	12-20	60-70
Adults (\geq 16 years)	90-140	60-90	12-20	50-100

All assessments (with and without assessment time) will be included in the data listing (Listing 16.2.9).

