16.4. EVALUATION OF EFFICACY

Refer to Sections 7.2.1 and 7.2.2 for the primary and secondary efficacy endpoints, respectively.

Efficacy evaluations will be performed using the FAS.

Efficacy will be assessed based on the metHb level and on the normalization of respiratory rate, heart rate and blood pressure after administration of ProvayBlueTM (single- or repeat dose).

The results will be descriptive only. A 95% CI for the responder rate will be presented for each of the primary and secondary endpoints. The results will be compared with historical methylene blue results to confirm that ProvayBlueTM's results are not unexpected.

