3.2. Analysis Population

The following analysis sets will be identified for data summary.

Enrolled Analysis Set: All patients who sign the informed consent or otherwise meet all local enrollment criteria for the study are considered to have enrolled.

Safety Analysis Set: The safety set will include all enrolled patients who are treated with at least 1 ProvayBlue™ infusion dose. The safety analysis set will be used for safety data summary. Specifically, the safety population will include all treated patients from the Interventional Study and the Observational Study.

Efficacy Analysis Set: The efficacy analysis set includes all safety analysis set patients who have at least 1 metHb assessment before and after ProvayBlue™ infusion and who are Primary cases. This analysis set will be used for efficacy endpoint evaluation.

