3.3. Endpoints

3.3.1. Efficacy Endpoints

The efficacy data summary will include the following endpoints:

- 1) Change from baseline in metHb after the first dose of ProvayBlue™ infusion.
The primary efficacy will be the number (%) patients with $\geq 50\%$ reduction in metHb based on the first available posttreatment assessment.
 - The following are secondary endpoints to support the primary endpoint.
 - i. Change in metHb posttreatment over time
 - ii. Time when 50% reduction in metHb is observed for the first time.
- 2) Change from baseline in vital signs (blood pressure, respiratory rate, and heart rate) after the first dose of ProvayBlue™ infusion.
 - The secondary efficacy will be the number (%) of patients with concomitant normalization of vital signs within 2 hours, inclusive, after the end of infusion of the first dose of ProvayBlue™
 - Time (hours) when the first incidence of normal vital signs was observed in patients who had abnormal baseline vital signs
- 3) In addition, 13 prespecified clinical signs and symptoms associated with methemoglobinemia and their intensity (as National Cancer Institute Common Terminology Criteria for Adverse Events [NCI-CTCAE] grade) before and after ProvayBlue™ treatment are collected. The presence/absence of those signs and symptoms will be treated as an 'other' efficacy endpoint since decrease and/or resolution of those signs and symptoms may be considered supportive of efficacy.

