5.2.1. Median Vital Signs within 2-Hour Post Treatment

Vital signs measurements, including systolic blood pressure, diastolic blood pressure, heart rate and respiratory rate, were taken at various time points and frequency. In order to synchronize the measurements, all vital signs measures taken within 2 hours will be pooled within each individual patient dataset to derive the median for the patient.

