5.2.3. Summaries of Vital Signs Change from Baseline

A summary table will include VS measurement and change from baseline by relative time frame with descriptive statistics of sample size, mean, standard deviation, 2-sided 95% confidence intervals, quartiles (25% tile, 50% tile [median], and 75% tile), minimum, and maximum. The table will also include number (%) patients whose vital signs are within the normal range (Table 14.2.2.1). Number (%) patients who had at least 1 incidence of normal vital signs within the 2 hours following the completion of first dose ProvayBlueTM infusion will also be presented.

Change in SpO₂ will be assessed in 3 categories, based on $\pm 2\%$ rule as follows

- 1) Increased if the difference (postbaseline – baseline) is >2
- 2) No Change if the difference (postbaseline – baseline) is within ± 2
- 3) Decreased if the difference (postbaseline – baseline) is <2

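### The planned vital-sign counts in SAP 5.2.3 do not separate patients who became normal from those never abnormal, and no planned output crosses vital signs with metHb response

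*SAP*

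**What the plan says.** SAP 5.2.2 names the endpoint: "The secondary efficacy will be the number (%) of patients with concomitant normalization of vital signs (as per the clinical context) within 2 hours". SAP 3.3.1 gives the same endpoint without the reference to clinical context. SAP 5.2.2 then assigns context to the narratives: "in the individual patient narratives, vital signs will be contextualized for comorbidity and other pertinent issues".

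Three summaries could score it:

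- SAP 5.2.1, a per-patient median: "all vital signs measures taken within 2 hours will be pooled within each individual patient dataset to derive the median for the patient".
- SAP 5.2.3, an in-range count: "number (%) patients whose vital signs are within the normal range (Table 14.2.2.1").
- SAP 5.2.3, a count of patients "who had at least 1 incidence of normal vital signs within the 2 hours following the completion of first dose".

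Only one vital-sign measure is limited by baseline status (SAP 3.3.1): "Time (hours) when the first incidence of normal vital signs was observed in patients who had abnormal baseline vital signs". Table 14.2.2.1 is run on the efficacy set, which takes safety-set patients "who have at least 1 metHb assessment before and after ProvayBlue™ infusion and who are Primary cases". Membership therefore requires metHb values but no vital-sign readings.

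Protocol 7.2.2 lists four secondary endpoints. Three pair a 50% metHb reduction with normalization of respiratory rate, heart rate and blood pressure: after a single dose, at 1 hour with vital signs at 2 hours, and after a second dose. Protocol 6.1 and 8.2 describe the post-marketing requirement in the same paired way. SAP Table 1 keeps the linked objective (normalization in patients whose metHb falls), but its endpoint row lists the signs one by one.

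**The concern.** Normalization is a change within a patient, from abnormal to normal. A percentage in range over the whole efficacy set is not that change, because anyone normal throughout counts as a success. The reader of the post-marketing report would want to know how many patients with abnormal vital signs recovered, and in how many of these metHb also halved. Neither number is a planned output.

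Both studies are uncontrolled and closed to enrollment. A scoring rule that is not written down would therefore be chosen with the data in hand.

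**Working it through.** The documents give no figure for this endpoint, so there is none to reproduce. The check sets the text side by side and sizes the effect with assumed inputs.

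**1. Link between endpoint and summary.** No sentence in SAP 3.3.1, 5.2.1, 5.2.2 or 5.2.3 says that the endpoint is scored on the median, the in-range count or the at-least-one count. The choice can matter. Take assumed adult heart rates of 112, 108, 104 and 98 in the window, with the SAP Table 4 range of 50-100. The at-least-one rule passes (98). The median is (108 + 104)/2 = 106, which fails.

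**2. Effect of no baseline restriction.** Let b be the share normal at baseline, s the share of those who stay normal, and r the share of abnormal patients who become normal.

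In-range share = b·s + (1 − b)·r, so its distance from r is b·(s − r).

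With s = 1 (assumed):

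| r (true normalization) | b = 25% | b = 50% | b = 75% |
|---|---|---|---|
| 0% | 25% | 50% | 75% |
| 30% | 47.5% | 65% | 82.5% |
| 70% | 77.5% | 85% | 92.5% |
| 90% | 92.5% | 95% | 97.5% |

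At b = 50% the gap runs from 50 points (r = 0) to 5 points (r = 90%).

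**3. Do before-and-after totals rescue it?** Table 14.2.2.1 also shows baseline. Assume 20 patients, 10 in range before and 13 after. If x abnormal patients became normal, then 13 − x normal patients stayed normal, and this must lie between 0 and 10. Hence x lies between 3 and 10. The same totals fit anything from 3/10 to 10/10 normalizing.

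**4. Effect on precision.** In that example with r = 30% and s = 1, the whole-set figure is 13/20 = 65% (exact 95% CI 41-85%). Among abnormal patients it is 3/10 = 30% (7-65%). The real set cannot exceed 7 + 24 = 31. The SAP does not give the number of Primary cases.

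**5. Joint outputs.** SAP 7.1 has seven 14.2.x outputs: three for metHb, two for vital signs, two for signs and symptoms. SAP 7.2 has 18 listings. None crosses metHb response with vital signs. With the 15/17 = 88% metHb response at 1 mg/kg from Protocol 6.5 and an assumed normalization rate v in the same patients, the joint share lies between 0.882 + v − 1 and v (for v below 0.882):

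- v = 30%: 18% to 30%.
- v = 60%: 48% to 60%.

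Even these bounds cannot be read from the planned tables. Table 14.2.1.1 covers only patients whose first post-dose metHb came before 2 hours, while Table 14.2.2.1 is planned on the whole efficacy set.

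**6. SpO2.** In SAP 5.2.3 *No Change* is a difference within ±2, and *Decreased* is printed as below 2. A difference of +1 meets both.

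**The case against.** Several points on the other side are fair.

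- *Concomitant* may already mean accompanying the metHb reduction. Protocol 13.1 and SAP Table 1 attach the word to each sign separately, after listing the metHb reduction first. On that reading the SAP's own count is joint, and what is missing is its output. This stands, which is why the meaning has to be stated.
- Normalization ordinarily presupposes abnormality, and the adjacent time-to-first-normal item is restricted that way. That is reasonable. But then the endpoint is neither 5.2.3 count, and no table is assigned to it.
- The in-range count is most naturally read as median-based, and both 5.2.3 counts will be reported, so neither can be quietly dropped. This mostly stands. The lack of a named rule would be a minor matter on its own.
- The report is mainly narratives with individual profiles and full listings. A reader could assemble shifts and joint status by hand from Listings 16.2.8 and 16.2.9. True, and it limits the consequence.
- The SpO2 slip is self-evident under the stated ±2 rule, and a minus sign may have been lost when the file was read. It still needs checking.

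A reader might infer that the SAP has dropped the joint endpoints against the protocol. The documents do not settle this. The precedence clause in SAP 1 covers the protocols' statistical section. The joint endpoints sit in Protocol 7.2.2, but Protocol 16.4 brings them in by reference. The SAP nowhere says that they were removed.

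A reader might also hold the sponsor to Protocol 16.4: "A 95% CI for the responder rate will be presented for each of the primary and secondary endpoints". That sentence is in the statistical section, so SAP 3.4, which offers 95% intervals where appropriate, governs.

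**Conclusion.** The point holds. As written, the two 5.2.3 percentages mix patients who were never abnormal with patients who became normal, and side-by-side totals do not give the within-patient shift. Three of the four Protocol 7.2.2 secondary endpoints have no crossed output, and the SAP does not say what became of them. SAP 3.3.1 and 5.2.2 leave the scoring rule and the meaning of *concomitant* open.

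The distortion in the percentage depends on assumed inputs. With half the patients normal at baseline and staying so, it is large if few abnormal patients recover (65% shown for a true 30%) and small if most do (95% for 90%). If baseline-normal patients leave the range, the whole-set figure could even be the lower one. The documents do not support a claim that the reported figure will be about double the true one.

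No error rate is affected, since the analysis is descriptive in at most 31 patients. The matter is which percentage is reported and when its rule is fixed. The sponsor should act on it, but it does not undermine the study.

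**What to change.** 1. Add a shift table to Table 14.2.2.1: baseline normal or abnormal against 2-hour normal, abnormal or missing, for each sign and for all signs together. Report the normalization count among patients with an abnormal baseline sign, with the number not evaluable and a 95% CI under SAP 3.4.
2. Before database lock, state whether the 2-hour median or the at-least-one reading is the endpoint and which is supportive, and define *concomitant*. Requiring all four medians in range is one option, not a necessity. Score the count on the SAP's stated ranges and keep clinical context in the narratives. Flag results by age group: Protocol 13.1 presents these ranges as examples, and some pediatric heart-rate bands are only 10 beats wide (60-70 at 3 to 5 years).
3. Add one joint count: a 50% metHb reduction at 1 hour under SAP 5.1.1 plus 2-hour normalization, with the number not evaluable and a note that the metHb value is interpolated. Otherwise state that the joint endpoints are dropped or appear only in narratives, including the second-dose one.
4. Correct the SpO2 category to a decrease of more than 2, that is, a difference below −2.

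The cost is a few sentences, one shift table and one count from data already collected. The downside is a smaller denominator, a wider interval and probably a less favourable percentage.

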5.2.3. Summaries of Vital Signs Change from Baseline

A summary table will include VS measurement and change from baseline by relative time frame with descriptive statistics of sample size, mean, standard deviation, 2-sided 95% confidence intervals, quartiles (25% tile, 50% tile [median], and 75% tile), minimum, and maximum. The table will also include number (%) patients whose vital signs are within the normal range (Table 14.2.2.1). Number (%) patients who had at least 1 incidence of normal vital signs within the 2 hours following the completion of first dose ProvayBlueTM infusion will also be presented.

Change in SpO₂ will be assessed in 3 categories, based on $\pm 2\%$ rule as follows

- 1) Increased if the difference (postbaseline – baseline) is >2
- 2) No Change if the difference (postbaseline – baseline) is within ± 2
- 3) Decreased if the difference (postbaseline – baseline) is <2

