- h. Vital signs will include: Systolic (SBP) and diastolic (DBP) blood pressure (mmHg), heart rate (beats per minute [bmp]), body temperature (°C or °F), respiration rate (breaths per minute), oxygen saturation by co-oximetry.
- i. If the patient is treated prior to consent, all available pre-treatment vital sign information should be retrieved where possible;
- j. Within 1 and 2 hours after the end of each ProvayBlueTM infusion (i.e. both Dose 1, Dose 2 and any additional dose if applicable).
- k. Additional (optional) parameters (for example blood gas) will be collected based on available data from patient standard of care.
- 1. Within 1 hour after the end of ProvayBlueTM infusion.
- m. If applicable (if the metHb level is acceptable within 1 hour after the end of Dose 1 ProvayBlueTM infusion, the repeat dose of ProvayBlueTM will not be needed).
- n. If applicable, in case of administration of additional doses of ProvayBlue at the discretion of the Investigator
- o. Collection of ECG data is mandatory at admission and approximately at 24 hours after the end of the last ProvayBlue™ infusion or just prior to discharge from the clinic if earlier than 24 hours. The collection of additional data will be based on available 12-lead ECG recordings performed as per patient standard of care as appropriate to determine general condition.
- p. ProvayBlueTM will be administered IV at a dose of 1 mg/kg over 5-30 minutes. If the methemoglobin level remains greater than 30% or if clinical signs and symptoms persist, a repeat dose of 1 mg/kg may be given 1 hour after the first dose. Depending on the clinical status of the patient, additional doses may be administered at the discretion of the Investigator. The data on these additional doses will be recorded in the study CRF.
- q. PK blood samples are to be drawn at the discretion of the Investigator. The suggested schedule of PK blood sampling is:
 - Approximately 1 hour after the end of each ProvayBlueTM infusion (i.e. Dose 1, Dose 2 and any additional dose if applicable);
 - Prior to Dose 2 (or any additional dose) ProvayBlue™ infusion (if applicable);
 - Approximately 24 hours post the end of the last ProvayBlue™ infusion, or just prior to discharge from the clinic if earlier than 24 hours.
- r. Collection of concomitant medications/medical procedures from PICD signature or the start of ProvayBlueTM treatment (whichever occurs sooner) until 10 to 15 days after the last administration of ProvayBlueTM;

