2. OVERVIEW OF STUDY OBJECTIVES AND ASSESSMENTS

2.1. Study Objectives and Endpoints

An overview of study objectives and study endpoints is provided in Table 1. The Observational Study was designed to mirror the objectives, endpoints, and data collection elements of the Interventional Study, with modifications to (1) reflect the nature of observational data, where the specific timing of procedures and measurements is driven by institutional standard care, not a study protocol, and (2) to streamline the protocol and study procedures where possible.

Table 1: Overview of Study Objectives and Endpoints

Protocol Number	PVP-2016003 (Interventional Study)	HQF-METHB-2018001 (Observational Study)
Primary Objective	To confirm that ProvayBlue™ after a single administration is efficacious in patients with acquired methemoglobinemia	To confirm that ProvayBlue™ is efficacious in patients with acquired methemoglobinemia
Secondary Objectives	
 • To evaluate the efficacy of a single dose of 1 mg/kg of ProvayBlue™; • To evaluate the efficacy of a second dose of 1 mg/kg of ProvayBlue™ to further reduce metHb levels when metHb is not fully reduced by a single dose; • To evaluate the normalization of the respiratory rate, heart rate and blood pressure of patients who achieve a reduction in metHb level within 2 hours of receiving the first dose of ProvayBlue™; • To confirm the safety and tolerability of ProvayBlue™ injection in patients with acquired methemoglobinemia. 	To confirm the safety and tolerability of ProvayBlue™ in patients with acquired methemoglobinemia
Study Population	Patients who present in hospital/urgent care setting diagnosed with acquired methemoglobinemia. The population may include pediatric and adult patients (males and females of all ages are included).	Patients who are diagnosed in any care setting with acquired methemoglobinemia. The population may include pediatric and adult patients (males and females of all ages are included).

Protocol Number	PVP-2016003 (Interventional Study)	HQF-METHB-2018001 (Observational Study)
		
Primary Treated Group: At least ten (10) patients who are treated for acquired methemoglobinemia that is symptomatic (eg, exhibiting sleepiness, cyanosis, dizziness) and/or with measured methemoglobin levels $>30\%$
 
Secondary Treated Group: Up to ninety (90) additional asymptomatic patients who are treated for acquired methemoglobinemia with measured methemoglobin levels $\leq 30\%$

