Safety Assessments	
 Physical examination; Vital signs; Hematology and biochemistry Electrocardiogram (ECG); Adverse events (AEs). 	Prevalence and nature of any adverse events occurring within 10 days of the administration of ProvayBlue™
Efficacy Endpoints	
 A reduction in metHb by 50% within 1 hour of dosing; Concomitant normalization of respiratory rate within 2 hours of the first dose of ProvayBlue™; Concomitant normalization of heart rate within 2 hours of the first dose of ProvayBlue™; Concomitant normalization of diastolic blood pressure (DBP) within 2 hours of the first dose of ProvayBlue™; Concomitant normalization of systolic blood pressure (SBP) within 2 hours of the first dose of ProvayBlue™. 	
 Time to reduction and magnitude of reduction in methemoglobin after administration of ProvayBlue™ for treatment of acquired methemoglobinemia. Time to normalization of the respiratory rate, heart rate, and blood pressure after administration of ProvayBlue™ for treatment of acquired methemoglobinemia Prevalence and nature of any adverse events occurring within 10 days

Protocol Number	PVP-2016003 (Interventional Study)	HQF-METHB-2018001 (Observational Study)
		
of the administration of ProvayBlue™
 
 • Prevalence of acquired methemoglobinemia cases by suspected causal agent • Resolution of methemoglobinemia-related symptoms during the index hospitalization
PK Endpoint	PK blood draws were planned and plasma concentrations of methylene blue and azure B were to be determined. However, PK data were not collected due to poor PK blood sample handling. Therefore, the PK endpoint will not be assessed.	None

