5.2. Change in Vital Signs

Vital signs change from baseline, including blood pressure, respiratory rate, and heart rate, will be derived for each patient. Baseline is the last vital sign measurement before a patient receives the first infusion of ProvayBlueTM.

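### The SAP's count of patients with at least one normal vital-sign reading, and its first-normal time, depend on how often each patient was measured and can credit a patient who did not change

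*SAP*

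**What the plan says.** SAP 5.2.2 names concomitant normalization of vital signs within 2 hours of the end of the first infusion as the secondary efficacy result. It also lists "Time (hours) when the first incidence of normal VS is observed in patients who have abnormal baseline vital signs". SAP 5.2.3 puts the number within the normal range in Table 14.2.2.1 and adds the "Number (%) patients who had at least 1 incidence of normal vital signs within the 2 hours following the completion of first dose". Baseline is a single value: "Baseline is the last vital sign measurement before a patient receives the first infusion" (SAP 5.2).

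On frequency, SAP 5.2.1 says that the measurements "were taken at various time points and frequency", and responds with a summary per patient: "all vital signs measures taken within 2 hours will be pooled within each individual patient dataset to derive the median for the patient". No text links that median to the at-least-one count, the first-normal time or the concomitant endpoint.

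The pooled studies were measured differently. The Interventional Study plans readings "Within 1 and 2 hours after the end of each ProvayBlueTM infusion" (Protocol, Appendix 2, footnote j). In the Observational Study "the specific timing of procedures and measurements is driven by institutional standard care, not a study protocol" (SAP 2.1), and its own endpoint is "Time to normalization of the respiratory rate, heart rate, and blood pressure after administration" (SAP Table 1).

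**The concern.** Baseline status rests on one reading, while post-dose status is normal if any one of an uncontrolled number of readings is in range. With no drug effect, the chance of at least one in-range reading still grows with the number taken. The percentage is therefore not comparable between patients, or between a study with about two planned readings in the window and a registry with none fixed.

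Three further gaps sit beside this:

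- The count is not limited to patients abnormal at baseline, so a patient who was normal throughout is counted.
- Neither 5.2.2 nor 5.2.3 says which reading decides concomitant normalization, or that systolic pressure, diastolic pressure, heart rate and respiratory rate must be normal together.
- The first-normal time has no rule for patients never seen normal, so a summary of observed times covers successes only. SAP 5.2.3 does not place it in a table.

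The stake is the vital-sign evidence. Protocol 6.1 and 8.2 list normalization of these signs within 2 hours among the minimal efficacy endpoints of the post-marketing requirement, and there is no control arm to show what monitoring alone would produce.

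**Working it through.** The plan gives no figure for this count or time, so there is nothing to reproduce.

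**Inputs.** From the documents: adult heart-rate range 50-100 (SAP Table 4), window 2 hours, single baseline reading, about 2 planned post-dose readings in the Interventional Study and no fixed number in the registry. Assumed: reading SD 8, a true rate that does not change, k = 2, 8 or 24 equally spaced readings, baseline reading at time 0 and above 100, correlation between readings 0.5 to 0.8 at 15 minutes and decaying with elapsed time.

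**Step 1, independent readings.** The chance that one reading is in range is q = Φ((100 − true rate)/8). At 110 this is Φ(−1.25) = 0.106. The chance of at least one in k is 1 − (1 − q)^k:

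- k = 2: 1 − 0.894² = 20%
- k = 8: 1 − 0.894⁸ = 59%
- k = 24: 1 − 0.894²⁴ = 93%

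Readings minutes apart are not independent, so these are upper figures.

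**Step 2, correlated readings.** Simulation of 200,000 unchanged patients per case, keeping those with an abnormal baseline. Each range spans correlation 0.8 to 0.5 at 15 minutes.

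| True rate | At least 1 normal, k=2 | k=8 | k=24 | Last reading only, any k |
|---|---|---|---|---|
| 105 | 35-45% | 53-78% | 62-89% | 24-26% |
| 110 | 16-20% | 29-46% | 36-62% | 10-11% |
| 120 | 1% | 3-4% | 4-8% | under 1% |

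**Step 3, the median of SAP 5.2.1.** In the same simulation the share called normal does not grow with k. At 110 it is about 10% with one reading and at most 6% with 2, 8 or 24. At 105 it is about 24-27% with one reading, 18-19% with 2 and 11-13% with 24.

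**Step 4, the time.** A patient truly normal from minute 20 and read every 120/k minutes is first seen normal at 120 minutes (k=1), 60 (k=2), 30 (k=4) and 20 (k=24). The patient is the same; the reported time differs sixfold.

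**The case against.** The strongest reply is that this count is a supplementary line. The named result is concomitant normalization, SAP 3.4 rules out inferential statistics, and only 31 patients were enrolled (7 + 24, SAP 1). Results are expected mainly as narratives (SAP 4), profiles are plotted per patient (5.2.4) and all readings are listed (5.2.2), so a lone in-range value would be visible. SAP 5.2.1 also recognises uneven frequency and derives a median for it. All of this stands, and it limits the consequence. It does not make the percentage interpretable, and the median helps only if a status rule uses it, which none does.

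Several stronger readings are tempting, and the documents do not support them:

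- A reader might infer that a closely monitored, unchanged patient will be counted. Such a patient can be counted; far from a limit the chance is small, as the 120 row shows.
- A reader might infer that the sickest patients were measured most often. Neither document says so.
- A reader might infer that the concomitant endpoint itself uses any normal reading. SAP 5.2.2 leaves the deciding reading unstated, which is a gap and not that rule.
- Holding correlation constant per reading, whatever the spacing, would give 88-99.9% at a true rate of 105 with 24 readings. That treats readings 5 minutes apart as no more alike than readings an hour apart, and overstates the effect.

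**Conclusion.** The point holds as a defect of definition. As written, the at-least-one count cannot fall, and the first-normal time cannot get later, as readings are added to a patient's record. The frequency of readings is uncontrolled and the schedule differs between the pooled studies. The size depends on how close the true value is to the limit: for an unchanged heart rate of 110, about 16-20% with 2 readings against 36-62% with 24; for 120, about 1% against 4-8%. These figures rest on the assumed SD, correlation, spacing and number of readings, none of which the documents give. The direction does not rest on them. The inclusion of patients normal at baseline and the missing deciding rule follow from the text alone. The summary is descriptive and has no hypothesis test, so this should be corrected, but it does not undermine the plan as a whole.

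**What to change.** In SAP 5.2.2 and 5.2.3:

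1. Limit the normalization count to patients with at least one abnormal sign at baseline, as the time measure already is, and state the denominator.
2. Decide status by one rule that does not inflate with frequency: all four signs in range on the per-patient 2-hour median of 5.2.1. Use the last complete set within 2 hours as a sensitivity analysis, since a median can miss a patient who normalizes late in the window.
3. Report the number of readings per patient in the window, by study.
4. Place time to normalization in Table 14.2.2.1. Keep patients who never normalize in the denominator, censored at their last reading, and state that the time is known only to the interval between the last abnormal and the first normal reading. An ordinary Kaplan-Meier curve at reading times would hide that.
5. Move any normal reading to Listing 16.2.9, or label it descriptive only.

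The cost is SAP wording and programming on data already collected. The normalization percentage will probably be less favourable, and some registry patients may lack a complete set of the four signs; their number should be reported.
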